[name] [name] and our study team led the pilot trial, the "Five-Plus Nuts and Beans" Trial which previously tested the impact of a community-based dietary intervention (Am J Prev Med, 2015). In this trial we tested the effectiveness of coach-directed dietary advice and assistance with weekly online ordering and purchasing of high potassium foods (\$30/week) delivered by a community supermarket to a neighborhood library, and tested other outcomes in urban African-American adults with controlled hypertension. We recruited patients from an urban primary care clinic in Baltimore MD and implemented the trial in partnership with a community supermarket and the Baltimore City Health Department. Advised to do so by our CAB/community partners, participants in the control group received a printed DASH diet brochure along with a debit account of equivalent value to that of the intervention (DASH-Plus) group at the same community supermarket. We randomized 123 participants and achieved 100% follow-up. At baseline, mean (SD) age was 58.6 (9.5) years, 71% were female, screening BP was 131.3 (14.7)/77.2 (10.5) mmHg, BMI was 34.5 (8.2) kg/m2, and 28% had diabetes. Self-reported fruit and vegetable intake of 3.5 (1.8) servings/day and estimated potassium intake of 2.7 (0.9) grams/day were well below recommended intakes. Compared to the control group, the DASH-Plus group increased self-reported consumption of fruits and vegetables by a mean (95% CI) of 1.4 (0.7, 2.1) servings/day and an estimated intake of potassium by 0.4 (0.1, 0.7) grams/day. DASH-Plus compared to control resulted in a significant increase in urine potassium excretion of 19% (1, 38)% and lower urine sodium excretion -20% (-38, -3)% (Figure 4). Also, there was a 14% reduction in albuminuria overall, and a 30% reduction among the subset of patients with significant albuminuria at enrollment. While we were underpowered to detect a BP effect at 8 weeks, we concluded that the Five-Plus intervention increased consumption of fruits and vegetables and excretion of urine potassium (an objective marker of potassium intake), and decreased excretion of urine sodium (an objective marker of sodium intake). Recognizing the needs of AAs with or at risk for CKD in Baltimore, and the lack of existing clinical trials of lifestyle modifications for AAs with CKD, we proceeded to develop an approach for AAs with both hypertension and mild/moderate CKD. Here, we describe plans for this intervention.

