# 2. Coaching DASH diet advice group (C-DASH):

#### Phase 1 (Months 0-4):

The C-DASH intervention will be a patient-tailored program, delivered by a study coach that is trained by a dietitian, which emphasizes key self-management behaviors – diet and self-monitoring. The C-DASH intervention will consist of a 1-hour one-on-one session with the study coach at randomization.

Thereafter, the study coach will meet with the participant at 1 month followed by phone calls only. Fifteen minute calls with participants will be weekly. During these interactions the study coach will build upon the participants' strengths and provide positive reinforcement of the progress being made.

Principal Investigator: [name], ScM

Application Number: IRB00122943

The C-DASH group will purchase \$30 worth of fruits, vegetables, nuts and beans through the study coach to reach a certain goal of potassium intake daily. The target for purchases will be a goal of 17,000 mg/week of potassium in order to increase dietary intake of potassium to 4.7 grams per day (DASH diet target) based on an estimated daily baseline intake of 2.4 g/d in this population. ShopRite will provide free packaging of food orders and foods will be delivered for pick up to Sisters Together And Reaching (S.T.A.R.) community center on [name] or by arrangement.

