Study duration and number of study visits required of research participants

The study will require 6 in person visits and up to 25 telephone (15 minutes only) calls over the course of 12 months.

b. Blinding, including justification for blinding or not blinding the trial, if applicable.

Participants will know their intervention assignments, as will study staff involved in delivering the interventions. However, study staff involved in follow-up data collection will be kept masked to participants' randomization assignments, and all intervention staff will be kept masked to participants' study measurements.

c. Justification of why participants will not receive routine care or will have current therapy stopped.

Participants will continue with their routine clinical care without interruption.

d. Justification for inclusion of a placebo or non-treatment group.

N/A. Our intervention group will be compared to a usual care group that receives \$30/week food allowance for 4 months.

- e. Definition of treatment failure or participant removal criteria. Participants who develop an exclusion criteria (e.g. stages 4 or 5 of CKD) will be removed from the study prematurely and documented correctly.
- f. Description of what happens to participants receiving therapy when study ends or if a participant's participation in the study ends prematurely.

If a participant chooses to withdraw from the research study, study personnel will inform the participant that compensation from the study will be held, due to prematurely ending participation.

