#### **Exclusion Criteria:**

• Cardiovascular (CV) event within 6 months

- Chronic disease that might interfere with trial participation (e.g. stage 4 or 5 CKD, eGFR <30 ml/min/1.73m^2)
- Unwillingness or inability to adopt a DASH-like diet
- Consumes over 14 alcoholic drinks per week
- Poorly controlled diabetes (Hemoglobin A1c >9%)
- Patients with a serum potassium >4.6 mEq/L
- Urine ACR  $\geq 1,000 \text{ mg/g}$
- Unable to participate in the study protocol based on the discretion of the Principal Investigator
- Pregnant or trying to become pregnant

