#### **Increase Potassium Levels:**

The study team will check the chemistry panel (serum potassium) to ensure potassium levels are in range. We will measure potassium levels throughout the study from blood samples.

c. Plan for reporting unanticipated problems or study deviations.

Risk events, problems, and deviations will be reported by the PI directly to the IRB.

d. Legal risks such as the risks that would be associated with breach of confidentiality.

There is a small potential risk to confidentiality. Most participant related data will be stored on an electronic database (encrypted and secured). If members of other Federal Agencies and IRB need to inspect potential trial records and documents, they will be release. Complete confidentiality cannot be guaranteed.

e. Financial risks to the participants.

There will be no financial risks to the participants. The study will pay for groceries, tests (urine and blood) and allowance from Klein's Shoprite stores of Maryland.

Principal Investigator: [name], ScM

Application Number: IRB00122943

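### Section 4.e removes from the study anyone who develops an exclusion criterion and nothing keeps their outcome visits going, which risks avoidable missing outcomes and weakens the intent-to-treat analysis

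*Combined protocol and SAP*

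**What the plan says.** Section 4.e, the protocol's whole answer on treatment failure and removal, reads: "Participants who develop an exclusion criteria (e.g. stages 4 or 5 of CKD) will be removed from the study prematurely and documented correctly". Section 4.f, where the form asks what happens when participation ends early, covers only people who choose to leave, who are told that "compensation from the study will be held, due to prematurely ending participation".

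Several Section 5 exclusions can arise after randomisation. They include eGFR below 30, a recent cardiovascular event, HbA1c above 9%, ACR of 1,000 mg/g or more, and "Patients with a serum potassium >4.6 mEq/L". Section 8 says of potassium only: "The study team will check the chemistry panel (serum potassium) to ensure potassium levels are in range". It does not mention removal.

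The Analysis Plan commits to intent-to-treat for the primary and secondary aims. It expects some dropouts and plans a mixed-effects likelihood analysis with multiple imputation under MAR, adjustment for baseline UAlb/Cr (said to make up for power lost to dropout), and sensitivity analyses for non-ignorable missingness. It does not mention removals required by the protocol.

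**The concern.** The sentence in 4.e speaks of the study, not of the diet or the food allowance. Taken plainly, a person who crosses one of these thresholds has no further outcome visits. The missing values would then be created by the protocol, in people who may be willing to attend.

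The loss may also be related to the comparison. ACR is the primary outcome, eGFR is closely tied to it, and serum potassium could plausibly rise more in C-DASH, whose weekly purchases have "a goal of 17,000 mg/week of potassium in order to increase dietary intake of potassium to 4.7 grams per day". At stake are some precision and possibly some bias in the month-4 contrast, on which the power calculation rests, and in the month-12 results.

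**Working it through.** **1. Can removal precede the month-4 outcome?** Yes. Follow-up Visit #1 and Table 1 schedule urine albumin and creatinine and blood chemistry at month 1. The paragraph on fasting serum lists only screening, month 4 and month 12. If that paragraph governed, scheduled potassium and eGFR could not affect the first month-4 urine sample, only later ones. HbA1c is first repeated at month 4, so it could affect at most the second month-4 urine sample and month 12.

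**2. Power.** Inputs from Section 7.c: difference 20%, SDs 63% and 53%, α = 0.05 (taken as two-sided), N = 150, with 148 stated for 80% power.
- Root-mean-square SD = √((63² + 53²)/2) = 58.2.
- Stated N: 2 × 58.2² × (1.96 + 0.84)²/20² = 133 per arm, 266 in total. With the factor 1 − 0.8² = 0.36 it is 48 per arm, 96 in total. Neither gives 148. That is a separate matter, so I use two SDs for the loss of power.
- SD implied by 148 at 80% power (two-sample t test): 43.1. Power is 80.5% at N = 150. Assumed losses of 5, 10 and 15% (N = 142.5, 135, 127.5) give 78.5, 76.2 and 73.8%.
- SD 58.2, unadjusted: 55.2% at N = 150 and 50.9% at N = 135.
- A 10% loss therefore costs about 4 points on either SD: 80.5 − 76.2 = 4.3 and 55.2 − 50.9 = 4.3.

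**3. Bias, illustrated with potassium.** The documents give no removal rates and no potassium distribution, so every input here is assumed: true mean 4.0 to 4.3 mEq/L, between-person SD 0.30, within-person SD 0.25, and entry only if the screening value is at most 4.6. The assumed extra rise in C-DASH is +0.02 to +0.1. A small rise is plausible because the pilot increased "an estimated intake of potassium by 0.4 (0.1, 0.7) grams/day" relative to control, whereas the present target implies 4.7 − 2.4 = 2.3 g/day.

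Share above 4.6 at month 1, over the range of means:

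| Arm and shift | Share |
|---|---|
| S-DASH, no shift | 4.5–14.0% |
| C-DASH, +0.02 | 5.0–15.3% |
| C-DASH, +0.05 | 5.9–17.3% |
| C-DASH, +0.1 | 7.7–21.4% |

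For those retained, the mean shift in log-ACR change is −r × s × φ(c)/Φ(c). Here c = Φ⁻¹(1 − p), p is the share removed, r is the correlation of the trigger with log-ACR change, and s is the SD of that change. I take s = 0.49, borrowing the 49% that Section 7.c cites from another CKD study. The bias is the difference between arms, back-transformed. Example with mean 4.0, +0.1 and r = 0.5: p = 0.077 against 0.045 gives 1.4%.

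Bias if only retained participants are compared, for r from 0.1 to 0.5:
- +0.02: 0.05–0.5%
- +0.05: 0.1–1.3%
- +0.1: 0.3–2.7%
- r = 0, or equal removal in both arms: 0

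In simulation with the +0.1 shift, imputing under MAR from month-1 ACR alone leaves 0.1–2.2%. Adding potassium to the model brings the result within 0.1 of full data. With the arms' removal rates reversed, a true 20% effect appears as 18.2–19.9%.

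**4. How far the inputs matter.** Letting the between/within SDs run from 0.25/0.15 to 0.30/0.35 widens S-DASH removal to about 1.3–19%. A separate null simulation (mean 4.2, SD 0.25, shifts +0.1 and +0.2, r = 0.3 to 0.5, baseline-adjusted analysis of retained participants) gave 1.6–6.0%. By the cruder formula (difference in removal rates) × (excess ACR change in those removed), 5% against 10–15% removed and an excess of 25 to 100 points gives 0.05 × 25 = 1.25 to 0.10 × 100 = 10 points. The upper end needs removed participants to do far worse than the rest.

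**The case against.** The strongest reply is that the plan already deals with missing data. Removal on an observed month-1 ACR is ignorable in a likelihood model that contains that ACR, and month-1 urine is scheduled. In one check with assumed inputs and a true 20% effect, analysing only those retained gave 19.8%, and the MAR model with month-1 ACR gave 20.1%, the same as full data. Baseline adjustment may recover the power. If the stated correlation of 0.8 is applied as a factor of 0.36 on the stated variance, power at 75 per arm is about 94% by normal approximation, and a 10% loss would matter little. Removal may also have been meant as removal from the intervention only. And the modelled trigger, potassium, is not the one that 4.e names. All of this stands, and it limits the size of the problem. It does not supply the outcomes that further visits would have given, and the imputation model is not specified, so nothing ensures that potassium or eGFR is in it.

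Four stronger readings are tempting, and the documents do not support them:
- That 4.e expressly ends data collection. This is the plain reading, but it is not stated. The consent form and Table 2, to which the design section refers, were not in the text I read.
- That intent-to-treat becomes impossible. Removed people can still be analysed as randomised with the data they have, and nothing says that earlier data are discarded.
- That everyone with raised potassium, or with "Unwillingness or inability to adopt a DASH-like diet", will be removed. Section 8 mentions no removal for potassium, and no adherence threshold after randomisation is given.
- That the rule favours C-DASH. The direction depends on which arm loses more people and on how the trigger relates to ACR change.

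**Conclusion.** The concern holds as a gap between 4.e and the Analysis Plan that should be closed. As written, the rule can create missing outcomes that are avoidable and possibly informative, and this weakens the intent-to-treat analysis without defeating it. The expected size is modest. For potassium shifts up to +0.1 and correlations up to 0.5, the bias is about 0–3% against the 20% target. It can go in either direction, and it is zero if removal is equal across arms or unrelated to ACR change. Harsher assumptions give more. The power cost of about 4 points is for an assumed 10% loss, before any gain from baseline adjustment. Confidence is medium, because every removal rate and potassium input is an assumption and the trigger that 4.e names, stage 4 or 5 CKD, was not quantified.

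**What to change.** Reconcile 4.e with the Analysis Plan by saying what removal from the study covers. Suggested addition to 4.e: *Meeting a criterion does not by itself end outcome follow-up. Unless consent is withdrawn or the participant cannot attend, the blood pressure, urine and blood visits already scheduled continue, and the participant is analysed in the assigned arm. Occurrences are reported by arm and reason.* When diet or food support stops is left to the investigators.

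For outcomes that are still missing, state in the Analysis Plan that the recorded trigger variables (ACR, potassium, eGFR) enter the imputation model. The passages on month-1 blood should be made to agree, since they determine which of these values exist before month 4.

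The cost is protocol and analysis-plan wording, with no tests or visits beyond the present schedule. The estimate will then include people who stopped the diet, as intent-to-treat implies.

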#### 5. Inclusion/Exclusion Criteria

#### Inclusion Criteria:

- Self-identified African American race
- Age 21 years or older
- Clinical diagnosis of hypertension and have a urine ACR of  $\geq$  30 mg/g with or without estimated GFR 30-59 ml/min/1.73m^2.
- Must be under regular care with their JHCP or JHOC physician (seen within the past 12 months).
- Must have a systolic blood pressure of <=160 mmHg and a diastolic blood pressure of

   =100 mmHg (average of two visits)
- Be on stable doses of antihypertensive medications for a minimum of two months prior to randomization.

Principal Investigator: [name], ScM

Application Number: IRB00122943

#### **Exclusion Criteria:**

• Cardiovascular (CV) event within 6 months

- Chronic disease that might interfere with trial participation (e.g. stage 4 or 5 CKD, eGFR <30 ml/min/1.73m^2)
- Unwillingness or inability to adopt a DASH-like diet
- Consumes over 14 alcoholic drinks per week
- Poorly controlled diabetes (Hemoglobin A1c >9%)
- Patients with a serum potassium >4.6 mEq/L
- Urine ACR  $\geq 1,000 \text{ mg/g}$
- Unable to participate in the study protocol based on the discretion of the Principal Investigator
- Pregnant or trying to become pregnant

# 6. Drugs/ Substances/ Devices

- a. The rationale for choosing the drug and dose or for choosing the device to be used. N/A
- b. Justification and safety information if FDA approved drugs will be administered for non-FDA approved indications or if doses or routes of administration or participant populations are changed.

N/A

c. Justification and safety information if non-FDA approved drugs without an IND will be administered.

N/A

# 7. Study Statistics

a. Primary outcome variable

**Primary Outcome Variable**: The primary outcome variable for this study is change in albuminuria.

b. Secondary outcome variables.

**Secondary Outcome Variable:** The secondary outcome variable for this study will be change in blood pressure, glucose, and weight.

c. Statistical plan including sample size justification and interim data analysis.

The trial has sufficient resources and adequate power to enroll 150 participants, who will be randomly allocated in equal proportions to the 2 groups: **Group A:** Self-Shopping DASH (S-DASH) diet advice group. **Group B:** Coaching DASH (C-DASH) diet advice group. The primary contrast is the difference in the percent change in (B vs. A) in urine albumin excretion (Urine Albumin to creatinine ratio, mg/g: UAlb/Cr mg/g). We used the standard deviation of the percent difference in the Urine Alb/Cr (post-pre/pre) of 63% and 53% in the intervention arm and the control arm, respectively. These variance estimates are from our pilot study (Five, Plus Nuts and Beans) published in 2016. The pilot trial enrolled African American patients with hypertension (similar to our eligibility criteria). Although albuminuria was not an eligibility criterion, 17 of 123 randomized had albuminuria (UAlb/CR ≥30 mg/g).

Principal Investigator: [name], ScM

Application Number: IRB00122943

Power calculations for our trial are based on a basic model that compares (4 month - baseline) differences among treatment groups (**Table**). The trial has 80% power to detect a treatment effect of 20% difference between arms at  $\alpha = 0.05$  if we enroll 150 participants. For this estimate, we set the correlation between

baseline and follow-up at 80%. This is a conservative estimate as the correlations of the log Alb/Cr between pre and post measurements in the pilot trial was 0.92 and 0.82 in the intervention and the control group, respectively. The weaker correlation in the intervention group would be expected, as variability in response to treatment in this arm would be greater. These treatment effects are achievable. In the pilot trial, the effect size noted was a ~39% difference (N=17) between the 2 arms in the subgroup with UAlb/Cr ≥30 mg/g at baseline. In the ACT Trial (a second trial of blood pressure management strategies in African Americans with uncontrolled

Net treatment	Power for	Sample
effect, % difference	single test	size
in UAlb/Cr	at $\alpha$ =0.05	needed
20%*	0.8	148
25%*	0.8	96
20% **	0.8	152

\*SD of %change is 63% and 53% in intervention and control arm, respectively (from 5+plus study).

hypertension) we observed a 31% difference between arms in the subgroup of participants with UAlb/Cr  $\geq$ 30 mg/g (N=34). Hence, our goal of achieving a 20% contrast is likely. As a secondary source of variance data we used SD of change data and sample size estimates published in 2016 (Sontrop JM et al., 2016) derived from a population of adults with CKD and based on a SD of change of 49% (less than what we observed) . In that study they report that the sample size needed to detect a 20% difference in UAlb/Cr would be N=152 (correlation was not reported). Secondary analyses of effects on blood pressure and weight will be evaluated at the nominal  $\alpha = 0.05$  level. This trial is not powered to see an effect on these secondary outcomes, yet analyses of effect of the intervention on protocol driven BP and weight measurements will be assessed.

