# **Analysis Plan**

This trial is a randomized trial that tests the effects of an innovative intervention against a minimal intervention on a selected set of outcomes. The primary contrast is (A vs. B) in Urine albumin excretion (**Primary Specific Aims**). For secondary analyses, we will test the contrast for reducing blood pressure, glucose, and weight (**Secondary Aim**). The analysis will be conducted under the intent-to-treat principle for both the Primary and the Secondary Aims before any supplemental analyses are conducted.

For the **Primary Aim**, groups will be compared using within-person differences in outcome levels obtained on those diets. Because we anticipate some dropouts (although there were none in the pilot), we will conduct our primary analysis using mixed effects modeling (likelihood) and multiple imputation approach under the missing at random (MAR) assumption. We will adjust for baseline UAlb/Cr which should increase our power and account for any power lost by drop-outs. We will then carefully examine all available data and build sensitivity analyses using clinically sensible missing scenarios to evaluate the potential impact by non-ignorable missing data. A parallel approach will be used for **Secondary Outcomes.** Distribution of data will be checked and transformed where appropriate. Other outcome variables will be analyzed with a similar approach. Adjustments for baseline variables will be made, where appropriate, in multivariable analyses. Ninety-five percent confidence intervals of the estimated mean differences will be constructed for each outcome.

\*\*SD of change of 49% (Sontrop JM et al., 2016

Principal Investigator: [name], ScM

Application Number: IRB00122943

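### The scale of the primary ACR analysis is not fixed, and on the plan's own percent-change scale 150 participants give about 56% power, not 80%

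*Combined protocol and SAP*

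**What the plan says.** Section 7 (Study Statistics), part c, defines the comparison: "The primary contrast is the difference in the percent change in (B vs. A) in urine albumin excretion". The variance inputs are on the same untransformed scale: "We used the standard deviation of the percent difference in the Urine Alb/Cr (post-pre/pre) of 63% and 53" per cent, for intervention and control in that order. Power rests on a "basic model that compares (4 month - baseline) differences among treatment groups", and the claim is: "The trial has 80% power to detect a treatment effect of 20% difference between arms" with 150 enrolled at alpha 0.05. The table gives a total of 148 for a 20% difference, 96 for 25%, and 152 for 20% with an SD of 49% taken from a cited study. The baseline-to-follow-up correlation is set at 0.80, and pilot correlations of log ACR (0.92 and 0.82) are given in support.

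The Analysis Plan describes the primary aim differently: "groups will be compared using within-person differences in outcome levels obtained on those diets". On the model it says: "we will conduct our primary analysis using mixed effects modeling (likelihood) and multiple imputation approach under the missing at random (MAR) assumption", with adjustment for baseline ACR. Then, directly after a sentence on secondary outcomes: "Distribution of data will be checked and transformed where appropriate". Results are to be reported as follows: "Ninety-five percent confidence intervals of the estimated mean differences will be constructed for each outcome".

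**The concern.** Percent change, difference in mg/g and log ratio are three different quantities. Eligible ACR runs from 30 to below 1,000 mg/g (section 5), so they can give different estimates and different p-values on the same data. Section 7 points to the first. The Analysis Plan's wording fits the second or is merely generic. The third appears only in the correlations. If the scale is settled after the data are seen, that choice may affect whether the one powered endpoint is positive.

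The power statement matters separately. The 80% figure is the justification for enrolling 150, and it should follow from the SDs printed beside it.

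**Working it through.** **Inputs (section 7).** SDs of percent change 0.63 and 0.53; differences 0.20 and 0.25; alpha 0.05; power 80%; 1:1 allocation; total 150 (75 per arm); r = 0.80. Sidedness is not stated. I take two-sided, in line with the planned 95% intervals.

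**1. The plan's own rows.** Total N = 2 × (1.960 + 0.842)² × (s₁² + s₂²)/d², where (1.960 + 0.842)² = 7.849 before rounding and s₁² + s₂² = 0.3969 + 0.2809 = 0.6778.

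- d = 0.20: 2 × 7.849 × 0.6778/0.0400 = 266.0
- d = 0.25: 2 × 7.849 × 0.6778/0.0625 = 170.2

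Power at 150 for d = 0.20: SE = √(0.6778/75) = 0.0951; 0.20/0.0951 − 1.960 = 0.144; power = 55.7%.

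**2. Does the correlation explain the gap?** An SD of change already contains the correlation. The only further factor that applies to it is the gain from baseline adjustment, (1 + r)/2. The other two factors are shown for completeness.

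| Variance factor at r = 0.80 | N for 20% | N for 25% |
|---|---|---|
| none | 266.0 | 170.2 |
| (1 + r)/2 = 0.90 | 239.4 | 153.2 |
| 2(1 − r) = 0.40 | 106.4 | 68.1 |
| 1 − r² = 0.36 | 95.8 | 61.3 |
| table in the plan | 148 | 96 |

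None gives 148 and 96. With the 0.90 factor, power at 150 is 60.2%. A total of 148 for a 20-point difference implies a common SD of 0.434, against √(0.6778/2) = 0.582 from the stated SDs. The ratio 148/96 = 1.54 is close to (0.25/0.20)² = 1.56, so the two rows do behave like an arithmetic percent effect, but with a smaller SD than the one printed.

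**3. The row quoted from the cited study.** With SD 0.49 and a log effect of ln(0.80) = −0.223: 4 × 7.849 × 0.2401/0.0498 = 151.4. On the arithmetic scale: 4 × 7.849 × 0.2401/0.04 = 188.5.

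**4. What the log scale would need.** The documents give no SD of change in log ACR, so each line below rests on an assumption about how 63% and 53% convert. The effect is ln(0.80), before baseline adjustment and drop-out.

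| Assumed conversion of 63%/53% | Total N | Power at 150 |
|---|---|---|
| lognormal, mean post/pre 1.2 in both arms | 133 | 85% |
| lognormal, median post/pre 1 in both arms | 149 | 80% |
| lognormal, mean post/pre 1 in both arms | 183 | 72% |
| read directly as log SDs | 214 | 65% |
| lognormal, mean 0.8 intervention, 1.0 control | 230 | 62% |

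**5. Does the scale matter?** Simulation: 75 per arm, lognormal change, true ratio 0.80, baseline truncated to 30–1,000 mg/g, 20,000 trials per scenario. The three values in each cell use log SDs of 0.515/0.454, 0.578/0.498 and 0.63/0.53 (the second, third and fourth conversions above).

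| More variable arm | Percent-change power | Log power |
|---|---|---|
| C-DASH | 63–64%, 49%, 37–38% | 79–80%, 71%, 64% |
| neither | 75%, 64–65%, 57–58% | 79%, 71%, 64–65% |
| S-DASH | 84–85%, 79%, 76% | 79–80%, 70–71%, 64–65% |

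The log powers should be read as unadjusted. Log change was simulated independently of baseline, so adjustment could gain nothing, and the values match the unadjusted formula. The two scales disagreed on p < 0.05 in 8–27% of trials. The same true 20% reduction reads as −17.5 to −30 points of percent change. With gamma-distributed change the order can reverse: percent change against log was 65/79%, 64/57% and 63/34% for C-DASH more variable, equal, and less variable.

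**The case against.** The strongest reply on scale is that section 7 does name one, percent change, and that the Analysis Plan's wording is generic. The transformation sentence sits between remarks on secondary and other outcomes and may not govern ACR at all. That stands in part: a reader might infer a flat contradiction, or a plan to analyse raw mg/g, and neither is stated. What remains is that no sentence says what the primary model is fitted to.

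A reader might also infer that the open scale inflates the false-positive rate. The documents do not support that. They describe a check of the distribution, not a choice of the smaller p-value. A simulated rule of that kind (log if the percent-change residuals fail a normality test, lognormal change, one assumed baseline shape) held type I error at 4.6–5.4%.

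A third inference is that the table mixes scales because 152 fits a log calculation. That row is quoted from a study whose scale is not stated and whose correlation was not reported. A one-sided arithmetic test gives about 150, so the log reading is only an inference. Likewise, 148 and 96 can be reached with unstated inputs, for example as per-arm numbers with 10% drop-out (133/0.9 and 86/0.9). The plan states no drop-out rate and presents its numbers as totals.

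Finally, fixing either scale in advance would cure the ambiguity, and log is not always the more powerful. Both points are right. Log is preferred because it has more power, under lognormal change, in the case the plan itself expects (the intervention arm more variable), and because a geometric mean ratio still reads as a percent difference.

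**Conclusion.** Two things hold. First, the scale of the primary mixed model is not fixed. Second, the stated power does not follow from the stated SDs on the plan's own scale: about 266 and 170 are needed, not 148 and 96, and 150 participants give about 56% (about 60% with baseline adjustment at r = 0.80), not 80%. This assumes a two-sided test and the normal approximation, with no loss to follow-up.

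A reader might go on to infer that the trial is underpowered on the log scale too. The documents cannot settle that. Illustrative conversions give a total N of roughly 133–230 and power at 150 of roughly 62–85% before adjustment, and the true value could lie outside. Choosing log therefore resolves the ambiguity of scale but does not itself explain or repair the failed rows; they have to be recomputed.

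**What to change.** In section 7 and the Analysis Plan, state that:

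- the primary analysis is the planned mixed model, with the planned imputation, on log(ACR), adjusted for baseline log(ACR);
- the primary contrast is C-DASH versus S-DASH at month 4, the time point of the power calculation, given as a geometric mean ratio with 95% CI;
- arithmetic percent change is descriptive;
- duplicate urine samples (the two screening samples, and the paired samples at months 4 and 12 in Table 1) are averaged on the log scale;
- the general transformation sentence applies to the other outcomes.

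Recompute the team's own two power rows with the pilot's SD of change in log ACR per arm, say how r = 0.80 enters, and restate the power at 150 without enrolling more. Label the scale of the 152 row or drop it. At the same time, settle which arm has the weaker pilot correlation: the text says the intervention arm, but the listed order gives that arm 0.92 and control 0.82.

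The cost is wording and one rerun from pilot data the team should already hold, with no new visits or samples. There are downsides. The effect becomes a ratio, and the restated power may fall below 80%. If C-DASH proves the less variable arm, percent change would have had about 5 to 12 points more power under lognormal change, and possibly more under other distributions.
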